Protocol and Statistical Analysis Plan

Title: Effect of the DentalVibe injections system on pain during local anesthesia injections in children
(0661-17-FB)

PI: [name]
NCT03374982
Approved 01-11-2018

Summary

The purpose of this study is to compare self-reported pain scale measurements using the Wong-Baker FACES pain rating scale from an experimental group (local anesthesia injection with DentalVibe system) and a control group (traditional local anesthesia injection with DentalVibe system turned off) in children. Eligibility: Children age 5-11 years old who require local anesthesia for bilateral dental treatment at UNMC pediatric dental clinic. Children must understand and speak English. Interventions and evaluations: Each patient will have two separate restorative appointments where the DentalVibe will be used during local anesthetic injections. One appointment the DentalVibe will be turned on and one appointment the DentalVibe will be turned off. After each injection the child will be shown the Wong Baker FACES Pain Rating Scale and asked to pick a face associated with their level of hurt during the injection. Follow-up: All children will be followed up with any necessary recommended dental treatment.

Purpose, Background and Rationale

The purpose of this study is to compare self-reported pain scale measurements using the Wong-Baker FACES pain rating scale from an experimental group (local anesthesia injection with DentalVibe system) and a control group (traditional local anesthesia injection with DentalVibe system turned off) in children.

An important aspect of behavior guidance in pediatric dentistry is the control of pain during dental procedures. There can be anxiety and discomfort associated with some dental procedures. Anxious patients feel more pain than less anxious patients.¹ Dental procedures can be carried out more effectively if a child is not in pain. The use of local anesthetic is generally indicated when teeth require restorative treatment or extraction. Dental injection is the dental procedure that produces the greatest negative response in children.² If a child experiences pain during a dental procedure, their future as cooperative dental patients may be damaged.³ Children who have traumatic dental experiences are more likely to avoid the dentist as an adult.^{4,5}

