More recently the DentalVibe has been proposed to reduce pain during local anesthetic administration. The device is handheld and delivers vibration to the tissues around the injection site. This device can replace the dental mirror or operator's finger to acts as a check and/or lip retractor. The DentalVibe allows for no changes in the traditional local anesthetic injection technique, patient position and time involved. In the study by Ching, the use of the DentalVibe injection system significantly reduced pain associated with infiltration injections of local anesthesia in adolescents.¹⁵ Studies of its use in children have had mixed results.¹⁶⁻¹⁷ The study by Raslan & Masri did not show significant reduction in pain with use of the DentalVibe. This study was conducted on subjects in a similar age group but only subjects with positive or absolute positive on the Fankl behavior rating scale were included. This raises the question of the influence of the DentalVibe on subjects with various levels of cooperation.¹⁸

This study will be a systematic replication of the study by Ching. The population will be younger and subjects will not be excluded for poor behavior. The purpose of this study is to compare self-reported pain scale measurements from an experimental group (local anesthesia injection with DentalVibe) and a control group (traditional local anesthesia injection with DentalVibe system turned off) in children ages 5-11.

Subjects

The justification for the inclusion of children in this research is that typically children experience discomfort during local anesthetic administration during dental appointments. 30 subjects between ages 5-11 should be an adequate number of subjects to complete the research. A power analysis will be performed to verify the total number of subjects needed to complete the research in order to achieve the scientific objectives of the study.

Inclusion Criteria

The specific inclusion criteria are children between the ages of 5-11 who require dental treatment that requires bilateral local anesthesia on the maxilla or mandible. Subject must understand and speak English.

Exclusion Criteria

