The specific exclusion criteria are that no children with the presence of medically or developmentally compromising conditions (autism, cerebral palsy, moderate/severe asthma); history of chronic disease (seizure disorder, cardiac disorder, hematological disease, endocrine disorder, liver disease, renal disease) and currently taking medication which contraindicated the use of local anesthesia. Non-english speakers will also be excluded. Subjects who require oral sedation or general anesthesia for treatment due to behavior or medical history will be excluded.

Methods

This study will be a systematic replication of the Ching study. The differences will be:

Age range of the subjects

Subjects will not exclude subjects with negative Frankl behavior ratings

All subjects will receive nitrous during both restorative appointment due to the age of the subjects.

Administration of nitrous oxide is commonly practiced in pediatric dentistry with patients of this age group. From McDonald & Avery (2016) eighty-five percent pediatric dentist use inhalation of nitrous

oxide and oxygen. It is used to reduce anxiety, produce analgesia, and enhance effective communication between a patient and health care provider.

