Up to 50 children between the ages of 5-11 years will participate in this randomized, controlled, split-mouth study. There will be no gender restrictions used in this study. Participants will be recruited from a continuous sample of patient seen at the UNMC pediatric dental clinic and will be selected based on their need for dental treatment. Each child will have 2 separate dental appointments. Written consent will be obtained from parent or guardian prior to first restorative appointment. Verbal consent will be obtained prior to second restorative appointment. [name] will be the provider for every patient. The same dental assistant will be used for each appointment. All treatment will be completed in the same private quiet room. Both [name] and the dental assistant will wear the same color scrubs and black lab jackets during all appointments. One appointment patient will receive local anesthetic dental injection with the DentalVibe turned on and at one appointment the child will receive local anesthetic dental injection with the DentalVibe off. Used strictly as a check/lip retractor. The child will be randomly assigned via a random number generator to either the DentalVibe on or off during the initial appointment. During the DentalVibe turned on appointment, the DentalVibe will be introduced to each child to make him/her familiar with the vibration sensation. All patients will receive 5 mins of O₂, then N₂O will be titrated up to 50%N₂O/50%O₂.

When appointment is complete the child will receive 5 mins of 100% O₂. At both restorative appointment a cotton tip applicator with 20% Benzocaine topical anesthetic gel (Patterson) will be administered for 1 min. 2% Lidocaine HCl with 1:100,000 epinephrine (Patterson Dental) will then be deposited using a medium-length (0.4mm) with 27-gauge short needles. Local anesthetic injections will be referred to as sleepy juice. Buccal and lingual infiltration will perform on the maxilla. Mandibular blocks will be performed on the mandible. One cartridge of local anesthetic will be used at each appointment. After administration, patient will be shown the Wong Baker FACES pain rating scale and asked to rate the amount of discomfort experienced during the injection by pointing to the face or number.

The following manuscript will be used:

Each face represents a person who has no hurt, or some hurt, or a lot of hurt.

Face 0 doesn't hurt at all.

Face 2 hurts just a little bit.

Face 4 hurts a little bit more.

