Face 6 hurts even more.

Face 8 hurts a whole lot.

Face 10 hurts as much as you can imagine, although you don't have to be crying to have this worst pain. Touch the face of the hurt you felt when I gave you the sleepy juice.

After child has rated pain [name] will continue with restorative treatment. The same process will be followed at the second appointment. Appointments will be scheduled 3-4 weeks apart.

The statistical methods to analyze the data will likely be a combination of measures of central tendency, descriptive stats, t-tests and correlations using SPSS version 2.2.

Risk

Potential risks are minimal. There is considered to be no more risk to a child beyond what is normally associated with local anesthetic injections. All potential participants will still require dental treatment requiring bilateral local anesthetic administration in the dental clinic. The only change in procedure for

consenting individuals will use the DentalVibe injections system to aid in local anesthetic administration. The DentalVibe system acts as a cheek and/or lip retractor which is often performed with the dental mirror or operator's fingers. [name] will monitor the subject's behavior by observation. This will help ensure the safety of the subjects.

Monitoring/Auditing/Analysis

[name] will conduct procedural checks in which the dentist (PI) implementing the procedures will be monitored to ensure appropriate consent is obtained and treatment protocol is being followed. The procedural fidelity checks will occur weekly.

[name] will perform ongoing data and safety analysis. She will administer the local anesthetic with the DentalVibe injections system and present the Wong-Baker FACES pain rating scale to the children after local administration.

Data analysis will occur every time a child is administered anesthetic. Data analysis will occur when the child is asked to evaluate his/her own pain rating.

Benefits

The potential benefits to the subject that may reasonably be expected from participation in the research is that less pain may be felt during local anesthesia injection. Potential benefits to society include the possibility of identification of an effective device to reduce pain during local anesthetic injections in children. This could lead to better behavior and more positive experiences in the dental clinic.

Recruitment

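### The plan has no rule for a child rated at only one visit: a paired t-test would drop that child, and if loss depends on visit-1 pain the estimate may be modestly biased and some power is lost

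*Combined protocol and SAP*

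**What the plan says.** In the combined protocol and SAP, the statistical paragraph of Methods is the only text on how the ratings will be compared: "The statistical methods to analyze the data will likely be a combination of measures of central tendency, descriptive stats, t-tests and correlations". It does not say whether the t-test is paired, which children form the analysis set, or how a child with one rating is handled.

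The design is also in Methods. "Each child will have 2 separate dental appointments", one with the device on and one with it off. "The child will be randomly assigned via a random number generator to either the DentalVibe on or off during the initial appointment". "Appointments will be scheduled 3-4 weeks apart".

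Four statements bear on who reaches visit 2:
- Methods: "Verbal consent will be obtained prior to second restorative appointment". Informed Consent repeats this.
- Purpose, Background and Rationale: "The population will be younger and subjects will not be excluded for poor behavior". Methods lists the admission of children with negative Frankl ratings as a deliberate difference from the study being replicated.
- Exclusion Criteria: "Subjects who require oral sedation or general anesthesia for treatment due to behavior or medical history will be excluded". No time point is attached.
- Purpose, Background and Rationale: "If a child experiences pain during a dental procedure, their future as cooperative dental patients may be damaged".

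Subjects calls 30 children adequate and defers the power analysis; Methods allows up to 50. No expected loss rate is given.

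**The concern.** A paired t-test works on the difference within each child, so a child with one rating contributes nothing. Yet order is randomised, so the visit-1 ratings are by themselves a randomised comparison of on with off. Dropping some of them discards information that the randomisation protects.

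The larger worry is which children go. If a painful first injection makes return less likely, the completers are selected on the outcome, and if the device works, more children treated off first are lost than children treated on first. At stake are the size of the estimate, the power of a small trial, and the representation of the less cooperative children whom this trial set out to admit. Without a rule, the handling of single ratings can be settled after the ratings are known, in a trial where the person giving the injection also collects the rating (Monitoring/Auditing/Analysis).

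**Working it through.** **1. The plan's own figure.** The sample size of 30 cannot be reproduced: alpha, power, effect, SD, within-child correlation and loss are all absent. Everything below rests on assumed inputs.

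**2. Power lost with the pairs.** Paired t-test, two-sided 0.05 (assumed), m pairs, m − 1 degrees of freedom, noncentrality d√m. A standardised paired effect of d = 0.53 gives 80% with 30 pairs. With 10%, 20% and 30% loss (27, 24, 21 pairs) power is 76%, 70% and 64%. With 50 enrolled, 10% or 20% loss (45 or 40 pairs) leaves 94% or 91%.

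**3. Direction.** The benefit is off minus on. Losing high visit-1 scores lowers the off mean among off-first completers, so their difference is too small. It lowers the on mean among on-first completers, so their difference is too large. Pooling cancels part of this. With no true effect and balanced order the two cancel exactly.

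**4. Bias, first set of assumptions.** Latent off mean 4, SD 3, correlation 0.5, latent effect 1.5, order 1:1, ratings on the 0, 2, …, 10 scale, 2,000,000 simulated children. The true FACES difference is 1.28. Of the children rating 8 or more at visit 1, 30% to 100% are lost, with 5% of the others.
- Complete pairs give 1.25 to 1.16. 1.25/1.28 = 0.98 and 1.16/1.28 = 0.91, so 2% to 9% low.
- Off-first completers give 1.17 to 0.80; on-first completers give 1.33 to 1.49.
- Check at the 100% end: a rating of 8 or more means a latent score of at least 7. Off first, that is P(Z ≥ 1) = 0.159, and loss is 0.159 + 0.05 × 0.841 = 20%. On first (mean 2.5), it is P(Z ≥ 1.5) = 0.067, and loss is 0.067 + 0.05 × 0.933 = 11%. The pooled value is (0.80 × 0.80 + 0.89 × 1.49)/(0.80 + 0.89) = 1.16, as simulated.
- If loss instead rises by 5% per rating point (17% overall), the result is 1.24, or 3% low.

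**5. Bias, other loss mechanisms.** Off mean 4.5, other inputs as in step 4, about 20% loss depending only on the visit-1 rating, 1,000,000 children. The full-data difference is 1.32.

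| Loss and the visit-1 rating | Complete pairs | Bias |
|---|---|---|
| Unrelated | 1.32 | 0% |
| Equal among all rating 2 or more | 1.33 | +1% |
| Linear | 1.30 | −2% |
| Logistic, slope 0.3 | 1.28 | −3% |
| Logistic, slope 0.6 | 1.25 | −5% |
| All rating 8 or more, no others (15% loss) | 1.20 | −9% |

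On an unbounded scale with linear loss the bias is −1% (1.49 against 1.50). A one-point shift in pain at visit 2 widens the range to −15% (1.08 against 1.27) through +1% (1.35 against 1.33). In the last row, a correlation of 0.3 gives 1.16 (−12%) and 0.7 gives 1.24 (−6%).

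**6. Keeping the single ratings.** A likelihood-type estimate that keeps all visit-1 ratings gives 1.31 to 1.35 against 1.32 in the tabulated cases. With correlation 0.7 in the last row it reaches 1.38 (0.06/1.32 = 5% high).

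In simulated trials of 30 children under the step 4 inputs (true difference 1.28):
- 1,500 trials per scenario, 8% to 36% loss: complete pairs averaged 1.20 to 1.26 and the mixed model 1.28 to 1.30. Power was 64.1% v 66.2%, 61.8% v 64.6%, 57.0% v 62.1% and 47.7% v 55.5%, so the model gains 2 to 8 points.
- A separate run of 500 trials per scenario: 1.18 to 1.26 for pairs, 1.24 to 1.26 for the model, about 1 to 3 points more power, and a similar false-positive rate.

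**The case against.** The strongest reply is that the bias is small. With an SD of 2.8 for the paired difference, the standard error with 30 pairs is 2.8/√30 = 0.51. The shifts of 0.03 and 0.12 in step 4 are 0.03/0.51 = 6% and 0.12/0.51 = 23% of one standard error. The larger needs every child rating 8 or more to disappear. There is no false-positive risk when the device does nothing and order is balanced. This stands, and it limits the weight of the point.

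Four stronger readings are tempting, and the documents do not support them:
- **That the device effect will be understated.** Direction and size depend on a loss mechanism that the documents do not give. Bias is nil when loss is unrelated to pain, and slightly positive when loss is flat above a rating of 2.
- **That the plan specifies a paired test.** It says only t-tests. An unpaired test would keep single ratings, but would ignore the pairing that the design creates. The plan must still say which is meant.
- **That the sedation exclusion removes children after randomisation.** It stands in a list of entry criteria, and nothing says that a randomised child is withdrawn under it. Its timing is unstated, which is an ambiguity and not a withdrawal rule.
- **That the protocol itself ties loss at visit 2 to pain at visit 1.** It says that later cooperation may be damaged. Its sentence on avoiding the dentist concerns adulthood, and Risk notes that participants still need the bilateral treatment, which is a reason to return. Pain-related loss is plausible, but no rate is given.

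**Conclusion.** The point holds as a conditional one. The plan is silent on single ratings, the natural test discards them, and loss before visit 2 is foreseeable. If loss depends on visit-1 pain, the complete-pair estimate may be biased, usually towards a modest understatement of a true benefit: about 0% to 9% under the main assumed inputs, and −15% to +1% if pain also shifts by a point between visits. Clear understatement needs loss concentrated at the highest ratings. The surer cost is power. A model that keeps all ratings recovers only part of it, about 1 to 8 points in the simulated trials, and enrolling nearer 50 would ease the power loss but not the bias. The change is worth making because it is a better method at almost no cost, not because the trial's conclusion is likely to turn on it. Means, SD, correlation, effect and loss rates are all assumptions.

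**What to change.** 1. Make the main analysis a linear mixed model of all FACES ratings, with condition and visit as fixed effects and child as a random effect, so that a single-visit rating counts.
2. Keep every randomised child in the analysis set.
3. Record the reason for each missing visit or rating, and report loss by order and by visit-1 rating.
4. State whether the sedation and general-anaesthesia exclusion applies only at entry or also later, and reconcile it with the statement in Purpose, Background and Rationale that poor behaviour is not a ground for exclusion.
5. Limit any worst-score sensitivity analysis to visits that were attended and injected but left unrated because of distress. Do not apply it to visits that never took place: scoring 10 for every visit 2 missed through distress assigns the worst score to a condition that the child never experienced. Under the step 4 assumptions it moves the estimate to 1.17 to 0.96, further from 1.28 than complete pairs.

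The cost is a few sentences in the SAP and one missing-reason field; SPSS, already named in Methods, fits the model. The downside is that the model assumes loss depends only on observed ratings, and it gains little if few children are lost.

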All subjects will be new or existing patients of the UNMC pediatric dental clinic. Research staff will have ethical access to potential subjects because [name] has a clinical relationship with the potential subjects. Participants will be recruited from a continuous sample of patients who are scheduled for new patient or recall appointments at the UNMC Pediatric Dental Clinic. The children's parent or guardian will be informed of the research. If parent/guardian chooses to have their child participate, the research will be further explained. A treatment appointment will then be made with [name]. If the parent/guardian chooses not to have their child participate, a treatment appointment will still be scheduled with [name] or one of the other providers.

Informed Consent

The location where informed consent will be obtained in the consultation room located in the UNMC pediatric dental clinic. The environment will be conducive to discussion. The consultation room is a private and quiet room located behind closed doors. [name] will be the only person involved in the process of consenting the parent or guardian about their child's participation in this study. Her responsibility will be to properly inform the parent or guardian about the research. Approximately 10-15 minutes will be allotted to the process of consent. The process of consent for parents or guardians who are likely to be more vulnerable to coercion or undue influence may include but are not limited to appointment of a subject advocate, involvement of the subject's family or friends, counselors or other confidants, reading the consent to the parents or guardians, and use of teaching aids. [name] will question the parents or guardian concerning his/her understanding of all the elements of informed consent. At the second treatment appointment [name] will get verbal consent for the child to continue to participate in the study before starting the appointment. During the appointment when the DentalVibe injection system is turned on, the DentalVibe will be introduced to each child to make

him/her familiar with the vibration sensation prior to use during local anesthetic injections. Tell-show-do will be used as a behavior guidance technique during all dental appointments.

References

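### The two-visit within-child design has no period term and no balanced visit order in its analysis plan; adding both is cheap and protects precision

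*Combined protocol and SAP*

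**What the plan says.** The design is a two-period crossover within the child. The Summary states "One appointment the DentalVibe will be turned on and one appointment the DentalVibe will be turned off", and Methods calls the study split-mouth: "Up to 50 children between the ages of 5-11 years will participate in this randomized, controlled, split-mouth study". The visits are separated in time ("Appointments will be scheduled 3-4 weeks apart"). Visit order is set at random: "The child will be randomly assigned via a random number generator to either the DentalVibe on or off during the initial appointment". No blocking, ratio or prepared order list is described.

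The whole statistical plan is one sentence near the end of Methods, saying that the methods "will likely be a combination of measures of central tendency, descriptive stats, t-tests and correlations". It does not say whether the t-test is paired, and it names no visit, period or sequence term.

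On sample size, the Subjects section says "30 subjects between ages 5-11 should be an adequate number of subjects to complete the research", Methods allows up to 50, and the power analysis is still to be done. No SD, effect size, alpha or power is given.

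The familiarisation step differs by condition. Methods says "During the DentalVibe turned on appointment, the DentalVibe will be introduced to each child to make him/her familiar with the vibration sensation", and Informed Consent repeats it.

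**The concern.** A child aged 5 to 11 may rate a second injection differently from the first, whatever the device does. The protocol's own background links anxiety to pain and describes injection as the dental procedure children react to worst, so a shift between visits is plausible, though its size is unknown.

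In a plain analysis of on-minus-off differences, such a shift enters with one sign for children who have the device on first and the opposite sign for the others. This has two consequences:

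- The differences spread more widely, so power falls.
- In the one trial that is run, the estimate moves by the shift multiplied by the order imbalance.

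A balanced order removes the second and a period term removes the first. Neither is in the plan.

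Carry-over is a separate matter. Children who have the device on first reach their off visit having already felt the vibration. If that changes their off rating, the estimated benefit changes too, and a period term cannot correct it.

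**Working it through.** The plan has no power figure to reproduce. N = 30 and N = 50 come from Subjects and Methods; everything else is an assumption, varied where it matters.

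**Assumptions.** The SD of within-child differences is 3 points, the test is two-sided at 5%, and the effect is 1.59 points, which gives 80% power for a paired t-test at N = 30 (noncentral t, 29 df) and 95.6% at N = 50. The visit effect p is 0.5, 1, 1.5 or 2 points.

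**Model.** D = effect ± p + error, with error SD 3 and the sign set by visit order. Under simple randomisation the unadjusted differences have variance 9 + p². With the period term the variance is 9.

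**Loss of precision.** Effective N = N × 9 / (9 + p²). For p = 1 and N = 30 this is 30 × 9/10 = 27; for p = 2 it is 30 × 9/13 = 20.8.

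**Power.** The unadjusted test under simple randomisation was simulated. The balanced order with period term uses the noncentral t with N − 2 df.

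| Visit effect p | Effective N of 30 | Power, N = 30, unadjusted | Power, N = 30, balanced + term | Effective N of 50 | Power, N = 50, unadjusted | Power, N = 50, balanced + term |
|---|---|---|---|---|---|---|
| 0.5 | 29.2 | 79.0% | 79.9% | 48.6 | 95.2% | 95.6% |
| 1 | 27.0 | 75.8% | 79.9% | 45.0 | 93.6% | 95.6% |
| 1.5 | 24.0 | 70.7% | 79.9% | 40.0 | 90.6% | 95.6% |
| 2 | 20.8 | 64.4% | 79.9% | 34.6 | 86.3% | 95.6% |

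Break-even at N = 30 is a visit effect of about 0.2 points.

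**Sensitivity to the SD.** The effect is re-solved each time for 80% power at N = 30. For a 1-point visit effect the gain in power (N = 30 / N = 50) is about 9 / 5 percentage points at SD 2, 4 / 2 at SD 3, and 2 / 1 at SD 4.

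**Six-level scale.** The ratings were rounded to 0, 2, ..., 10, assuming an off mean of 5, a visit SD of 3 and a correlation of 0.5. For p = 0.5/1/1.5/2 at N = 30, power is 73/71/65/60% unadjusted against 75/74/74/74%. The pattern holds.

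**Order imbalance.** With Binomial(N, 0.5), a split of 18:12 or worse occurs in 36% of lists at N = 30, 20:10 or worse in 10%, and 30:20 or worse in 20% of lists at N = 50. The estimate moves by p × (n₁ − n₂)/N. At 18:12 or 30:20 that is 0.2p, or 0.2 to 0.4 points for p = 1 to 2; at 20:10 it is 0.33p.

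**Type I error of the unadjusted test.** Averaged over all lists it is about 5%. Conditional on the split at N = 30, for p = 1 / 2, it is 3.9 / 1.9% at 15:15, 5.2 / 5.2% at 18:12, and 7.5 / 12.8% at 20:10. Balance without the term therefore makes the test conservative.

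**Carry-over.** If the off rating after an on visit is lowered by c and order is balanced, half the children are affected, so the estimate becomes 1.59 − c/2. That is 1.34 for c = 0.5 and 1.09 for c = 1, with or without the period term.

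**The case against.** The strongest reply is that nothing is wrong with the plan as it stands. Order is randomised, so it is balanced in expectation; the paired t-test is valid; and movement of the estimate with order imbalance is chance variation that the standard error already reflects on average. The raised type I error at a 20:10 split belongs to the worst tenth or so of lists and should not be read as bias. All of that stands, and it is why this is an improvement rather than a correction.

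The size of the benefit also rests on a visit effect the documents do not give. The protocol holds much constant across visits: provider, assistant, room, clothing, nitrous oxide, topical gel and script. That controls the setting, but it does not stop a child from reacting differently to a second injection. The dependence on SD is real too, and the range above shows that it cuts both ways.

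A random number generator could be used to build a blocked list, and the analysis wording is openly provisional. Both are true, but the text does not say that the list is blocked.

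Finally, one can say the more basic gap is that the t-test is not stated to be paired. That is fair. If it were run unpaired, with a visit SD of 3 and a correlation of 0.5, power at N = 30 would be about 53% rather than 80%. Naming a within-child analysis closes that gap as well.

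**Conclusion.** The point holds as an inexpensive improvement to a valid but loosely specified analysis. With an SD of differences of 3, balanced order plus a period term gains about 1, 4, 9 and 16 percentage points of power at 30 children for visit effects of 0.5, 1, 1.5 and 2 points. At 50 children the gains are about 0.4, 2, 5 and 9. The gain becomes material from a visit effect of about 1 point, is larger for a smaller SD, and is absent if ratings do not shift between visits. SD, effect and visit effect are all assumed. Carry-over from the on visit is a limitation that the change does not remove.

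**What to change.** 1. State the primary analysis as the within-child on-minus-off difference adjusted for period, two-sided at 5%: a mixed model with treatment and period as fixed effects and child as a random effect. For complete pairs this equals the mean of the two order-specific mean differences.
2. Prepare the order list in advance in permuted blocks of varying size, so that on-first and off-first stay close to equal and the single provider cannot guess the next order.
3. Report mean ratings by order and visit, and say that the period term does not remove carry-over from the on visit.
4. Base the pending power analysis on this model.

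The cost is a few sentences and a prepared list. One degree of freedom is lost: with balanced order and no visit effect, power at N = 30 falls from 80.0% to 79.9%, and by less than 0.1 percentage points at N = 50. The term without balanced order would cost about 1.5 percentage points at N = 30, and balance without the term leaves the test conservative, so the two should be adopted together. Varying blocks and missed second visits will give near rather than exact balance; the resulting loss should be small.

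### Do the two sample sizes and the wording on continuous data analysis let the results decide when the trial stops?

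*Combined protocol and SAP*

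**What the plan says.** The number of children appears in two places. Subjects says "30 subjects between ages 5-11 should be an adequate number of subjects to complete the research" and adds "A power analysis will be performed to verify the total number of subjects needed", without a date or inputs. Methods says "Up to 50 children between the ages of 5-11 years will participate in this randomized, controlled, split-mouth study".

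Under Monitoring/Auditing/Analysis, one member of the team "will perform ongoing data and safety analysis". The same person gives the injections and presents the pain scale. Two sentences on timing follow: "Data analysis will occur every time a child is administered anesthetic" and "Data analysis will occur when the child is asked to evaluate his/her own pain rating".

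The analysis itself is described at the end of Methods: "The statistical methods to analyze the data will likely be a combination of measures of central tendency, descriptive stats, t-tests and correlations". No alpha, sidedness, interim test or stopping rule is given anywhere.

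**The concern.** With the size open between 30 and 50, and data analysis said to happen at every injection, the plan can be read as allowing a running comparison of device-on and device-off scores, with enrolment closed when that comparison is favourable. The person reviewing the data also treats the child, so she knows whether the device is on when each score arrives.

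Two things would be at stake:

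- **Type I error.** Repeated testing at an unadjusted 5% level, stopping at the first significant result, rejects a true null more often than 5%. Even if nobody did this, a reader of a positive result could not tell from the protocol that the final number was fixed independently of the scores.
- **Precision.** Thirty pairs can miss a difference that 50 pairs would detect, so the choice of number matters for how a null result is read.

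**Working it through.** **1. Can the stated number be reproduced?** No. The documents give no alpha, power, effect size or SD, so there is no calculation behind 30 or 50 to check. It also follows that the plan claims no power that its design fails to deliver.

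**2. Do the two numbers conflict?** One is an expected adequate number and the other an upper limit, so any total from 30 to 50 satisfies both. A ceiling above the expected number is normal when each child must return 3-4 weeks later and the study dentist "will get verbal consent for the child to continue to participate in the study before starting the appointment". To finish with 30 completers, enrolment must be 30/(1 − dropout). Dropout is not given in the documents; assumed values give:

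- 5%: 30/0.95 = 31.6, so 32 children
- 10%: 30/0.90 = 33.3, so 34 children
- 20%: 30/0.80 = 37.5, so 38 children

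All lie under 50. Enrolling 50 would still leave 30 completers at a dropout of 1 − 30/50 = 40%.

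**3. What does the choice of number change?** Assume a paired t-test, two-sided 5%, 80% power. The normal approximation to the detectable standardised difference is (1.960 + 0.842)/√n:

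- n = 30: 2.802/5.477 = 0.51; exact noncentral-t value 0.53
- n = 50: 2.802/7.071 = 0.40; exact noncentral-t value 0.40

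At an assumed SD of the paired difference of 3 points (range 2-4), these are 0.529 × 3 = 1.6 points (1.1-2.1) and 0.404 × 3 = 1.2 points (0.8-1.6). For a true difference of 0.4 SD, power is 56% with 30 pairs and 79% with 50. The question is the same at both sizes; only the precision differs.

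**4. What would result-dependent stopping cost?** Simulation under the null, paired t-test at nominal two-sided 5%, stopping at the first significant result in either direction:

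| Looks | Rejection rate |
|---|---|
| 30 only, or 50 only | 5.0% |
| 45 and 50 | 6.5% |
| 30 and 50 | 8.0% |
| every child, 30 to 50 | 12.5% |
| every child, 10 to 50 | 22.4% |

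If early stopping is for benefit only, with a test at 50 otherwise, the rate is 6.5% for looks at 30 and 50, and 8.7% for a look after every child from 30. These are illustrations, not bounds. Extending from 30 to 50 only when p at 30 lies between 0.05 and 0.10 gives 6.0%. Replacing normal differences by differences of discrete 0-10 face scores (assumed distribution) leaves the figures nearly unchanged: 8.0% for looks at 30 and 50, and 12.5% for every child from 30.

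**5. Does the plan describe any of these rules?** Setting the two timing sentences side by side:

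- The first places data analysis at each administration of anaesthetic. The second places it when the child is asked for a rating. Both describe the same few minutes in the chair, and what happens then is that a score is obtained and written down.
- A test of on against off cannot be updated at each administration. Each child has two injection appointments, and only the second completes a pair. With 30 children there are 60 appointments and 30 pairs, so half of the occasions add no on-off difference.
- The summary statistics, t-tests and correlations appear separately in Methods, with no link to enrolment.
- The only method named for settling the total is the power analysis.

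On this reading stopping does not depend on the scores, and the first row of the table applies.

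**The case for a change.** The strongest case for acting starts from silence. No section fixes a final number, defers the comparison of conditions, or separates the person who sees each score from the person who reviews the data. A target with a ceiling still needs some rule for where between them to stop. Read literally, analysis at every injection would begin with the first children, and looks from child 10 onward would give about 22%, well above the 8-12.5% illustrated for a first look at 30. Subjects reports that enrolment should be adequate at 30, while the background describes earlier results in children as mixed, so a null result from only 30 might settle little. A sentence or two would close the gap at almost no cost.

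The factual part stands: there is no single target, the power analysis has no date or inputs, and the term data analysis is used loosely. The inference from it does not. Few short protocols expressly exclude stopping on results, so the absence of such a sentence is weak evidence that it is intended. The inflated rates need a rule that appears nowhere in the plan, and the start at child 30 is itself borrowed from the Subjects section, which does not call it a look. The power point shows that more children give more precision, which is true at any size. It does not show that 30 falls short of a stated aim, because no target difference is stated.

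**Conclusion.** No change to the plan follows. An expected 30 and a ceiling of 50 are compatible, the plan names the step that is to settle the total, and the monitoring sentences are most naturally about recording each rating and watching safety. Nothing makes enrolment depend on the scores, so a single final test keeps its nominal level (5% under the assumed two-sided paired t-test).

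What remains is missing detail that analysts would ordinarily supply: do the power analysis, recruit to the resulting number within 50, and compare the conditions when the data are complete. Within the stated range, the practical consequence is a detectable difference between 0.53 SD (30 completers) and 0.40 SD (50 completers).

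This conclusion rests on reading data analysis at the chairside as data capture, which the text supports but does not state outright. If enrolment were in fact stopped on the scores, the rates of about 8% to 12.5% (first look at 30) or about 22% (first look at 10) would become relevant. That would be a matter of how the trial was conducted, not of a rule in this plan.
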